## 1 Modification History

Version	Effective Date	Author of Modification	Reason for Change
1.0	01/APR/2020		N/A – First Version
2.0	19/JUN/2020	PPD	Incorporation of Protocol Amendment 2; Assignment of concomitant medication; COVID-19 related modifications; combination of 2 nd and 3 rd interim analysis; editorial changes.

## 2 List of Abbreviations

Abbreviation	Definition
AE	Adverse Event
CCI	CCI
AESI	AE of Special Interest
CCI	CCI
ATC	Anatomical Therapeutic Chemical
AUC 0-tau	Area under the concentration-time curve in one dosing interval
BMI	Body Mass Index
C4	Complement Component 4
CDISC	Clinical Data Interchange Standards Consortium
CL tot	Total Systemic Clearance
C max	Maximum Concentration
COVID-19	Corona Virus Disease 2019
CI	Confidence Interval
CSR	Clinical Study Report
EMA	European Medicines Agency
ESP	External Service Provider
eCRF	Electronic Case Report Form
FDA	Food and Drug Administration
FXII(a)	(Activated) Factor XII
HAE	Hereditary Angioedema
CCI	CCI
ICH	International Conference on Harmonisation
IDMC	Independent Data Monitoring Committee
CCI	CCI
IRT	Interactive Response Technology
ISR	Injection Site Reaction
ITT	Intent-to-Treat Population
IV	Intravenous(ly)
MCMC	Markov-Chain Monte Carlo
CCI	CCI

Abbreviation	Definition
MedDRA	Medical Dictionary for Regulatory Activities
CCI	CCI
PK	Pharmacokinetic
PP	Per-Protocol Population
PT	Preferred Term
CCI	CCI
q2wk	Administered Every 2 Weeks
q4wk	Administered Every 4 Weeks
SAE	Serious AE
SAP	Statistical Analysis Plan
SC	Subcutaneous(ly)
SD	Standard Deviation
CCI	CCI
SOC	System Organ Class
T 1/2	Terminal Elimination Half-Life
TEAE	Treatment-Emergent Adverse Event
TEE	Thromboembolic Event
TFL	Tables, Figures, and Listings
T max	Time of C max
V z	Volume of Distribution During the Elimination Phase
CCI	CCI

### 3 Purpose

This SAP provides a detailed and complete description of the planned statistical analyses for the Independent Data Monitoring Committee (IDMC), the interim, and final analysis of the study CSL312\_2001 to support the Clinical Study Report (CSR). Mock tables, figures, and listings (TFL) shells will be provided in separate supporting document.

This SAP complies with the International Conference on Harmonisation (ICH) Harmonised Tripartite Guideline Topic E9, Statistical Principles for Clinical Trials. It is based upon the following study documents:

- Study Protocol Amendment 2 (dated 20 March 2020);
- Electronic Case Report Form (eCRF) (dated 11 May 2020).

The "Guideline on Missing Data in Confirmatory Clinical Trials" (European Medicines Agency [EMA] dated 2 Jul 2010) is relevant for analysis methodologies for missing data for the primary efficacy comparison.

Further detailed Pharmacokinetic (PK)-CCI analyses will be described in the Modeling and Simulation Analysis Plan.

All decisions regarding the IDMC, interim, and final analysis of the study results, as defined in SAP 1.0 document, have been made within 2 months after the first subject will be entered the Run-in period.

SAP 2.0 was issued following Protocol Amendment 2.

### 4 Study Design

#### 4.1 Study Design

This is a multicenter, randomized, placebo-controlled, parallel-arm, phase 2 study to investigate the clinical efficacy, PK, and safety of CSL312 as prophylaxis to prevent hereditary angioedema (HAE) attacks in subjects with C1-esterase inhibitor (C1-INH) deficiency HAE or HAE with normal C1-INH and factor XII or plasminogen gene mutation (FXII/PLG). As presented in Figure 1, the study consists of a Screening Period, a Run-in Period, 2 treatment periods, and a Follow-up Period.

The following interim analyses are planned, with the sequence depending on subject recruitment:

- after the last C1-INH subject who participated in the blinded part of the study has completed Treatment Period 1;
- after the last C1-INH subject who participated in the open-label part receiving **600** mg CSL312 and the last FXII/PLG subjects of the study have completed Treatment Period 1

All available data will be reported in each of the interim analyses. For details on the interim analyses see Section 4.6.1.

[figure not shown]
Three IDMC analyses are planned around following time points:

- First IDMC: December 2018;
- Second IDMC: end of February 2019;
- Third IDMC: end of May 2019 or beginning of June 2019.

Further IDMC analyses during Treatment Period 2 will be conducted with the first one planned after the last subject will have entered Treatment Period 2 and will have completed 3 months in Treatment Period 2. Subsequent IDMC analyses will be planned around every 4 months.

The IDMC intervals may be adjusted during the study depending on the enrolment rate. IDMC meetings may also be conducted upon request.

**Figure 1 Study Overview**

**Abbreviations:** q2wk = administered every 2 weeks; q4wk = administered every 4 weeks.

**Footnotes:**

- a An overview of the Run-in Period is presented in protocol section 3.1.2.
- b An overview of Treatment Period 1 is presented in protocol section 3.1.3.
- c An overview of Treatment Period 2 is presented in protocol section 3.1.4.
- d An overview of the Follow-up Period is presented in protocol section 3.1.5.
- e Subjects may use the medication of their choice to treat HAE attacks experienced during the study if that medication has previously been shown to be effective. Investigators should ensure that participating subjects are capable of managing their HAE attacks.
- f C1-INH HAE subjects will be assigned to receive 100 mg CSL312 q2wk, only after 32 subjects with C1-INH HAE are first randomly assigned to receive placebo or 100 mg, 200 mg, or 300 mg CSL312 q4wk.
- g Subjects will receive treatment with investigational product in a blinded manner. These subjects will receive an initial intravenous (IV) loading dose of investigational product in Treatment Period 1 before receiving investigational product q4wk.
- h Subjects will receive treatment with CSL312 in an open-label manner.
- i Subjects will receive treatment with CSL312 in an open-label manner. These subjects will receive an initial IV loading dose of investigational product in Treatment Period 1 before receiving investigational product q4wk.
- j All C1-INH HAE subjects receiving the 300 mg dose will have their dose reduced to 100 mg q4wk SC at their next scheduled study visit.

### 4.1.1 Run-in Period

After Screening, eligible subjects will enter the Run-in Period which will last at least 4 and up to 8 weeks. The HAE attacks recorded during Run-in will serve as subject's comparator to the number of attacks which occur under treatment.

Subjects are not permitted to use routine prophylaxis to prevent HAE attacks during the Run-in Period; however, subjects may use on-demand HAE therapy to treat emerging HAE attacks if that medication has previously been shown to be effective.

To enter Treatment Period 1 subjects must have participated in the Run-in period for a minimum of 4 weeks, and among other inclusion and exclusion criteria (see Protocol section 4.1.3) during that time:

- experienced  $\geq 2$  HAE attacks within a consecutive 4-weeks period during Run-in (subjects with C1-INH HAE);
- experienced  $\geq 1$  HAE attack during Run-in (subjects with FXII/PLG HAE).

### 4.1.2 Treatment Period 1

Subjects who are eligible should enter Treatment Period 1 no later than 14 days after Week 9 (Day 57) of the Run-in Period.

Treatment Period 1 will last for around 13 weeks. Subjects may complete the study after Treatment Period 1.

#### *Subjects with C1-INH HAE*

The first 32 eligible subjects with C1-INH HAE will be randomly assigned to receive treatment (■ mg CSL312 q4wk; ■ mg CSL312 q4wk; ■ mg CSL312 q4wk; placebo q4wk) with investigational product in a ratio of 1:1:1:1 during Treatment Period 1 as described in detail in Section 4.4. Subjects will receive a single intravenous (IV) loading dose of investigational product followed by three subcutaneous (SC) doses, depending on the randomized treatment arm in the following way:

- A single loading dose of ■ mg CSL312 IV followed by ■ mg CSL312 administered every 4 weeks (q4wk) (SC).
- A single loading dose of ■ mg CSL312 IV followed by ■ mg CSL312 q4wk SC.
- A single loading dose of ■ mg CSL312 IV followed by ■ mg CSL312 q4wk SC.

- A single loading dose of placebo IV followed by placebo q4wk SC.

For these first 32 subjects with C1-INH HAE, Treatment Period 1 will be conducted in a blinded manner, and the investigational product will be volume-normalized to maintain the blind.

After the first 32 subjects with C1-INH HAE are randomly assigned to study treatment, up to an additional 8 subjects with C1-INH HAE will be assigned to receive [REDACTED] mg CSL312 administered every 2 weeks (q2wk). [REDACTED]. For these C1-INH HAE subjects, Treatment Period 1 will be conducted in an open-label manner and the investigational product will not be volume-normalized.

#### *Subjects with FXII/PLG HAE*

Up to 10 eligible subjects with FXII/PLG HAE will be assigned to receive a single loading dose of [REDACTED] mg CSL312 IV followed by [REDACTED] mg CSL312 q4wk. For these FXII/PLG subjects, Treatment Period 1 will be conducted in an open-label manner and the investigational product will not be volume-normalized.

### **4.1.3 Treatment Period 2**

All subjects who participated in Treatment Period 1 may participate in Treatment Period 2. Treatment Period 2 will last for at least 44 weeks, or until another CSL312 study is opened for subjects to join, or until the current study is discontinued. Treatment Period 2 will be conducted in an open-label manner for all subjects. Subjects will be re-randomized or continue the treatment received in Treatment Period 1 as described in detail in Section 4.4.

Dose modification details for Treatment Period 2 are presented in Section 4.3.2. All C1-INH HAE subjects receiving the [REDACTED] mg dose will have their dose reduced to [REDACTED] mg q4wk SC at their next scheduled study visit, effective with Amendment 2.

### **4.1.4 Post-Treatment Follow-up Period**

[figure not shown]
Subjects will attend a Follow-up Visit ~2 weeks after each subject's final treatment period visit; however, the Follow-up Visit may be waived in place of a telephone contact, at the discretion of the investigator.

## 4.2 Objectives and Endpoints

Objectives	Endpoints
Primary	
The primary objective of this study is to evaluate the efficacy of CSL312 in the prevention of HAE attacks in subjects with C1-INH HAE.	Time-normalized number of HAE attacks.
Secondary	

 
1. To further evaluate the efficacy of CSL312 in subjects with C1-INH HAE.
 
2. To evaluate the PK of CSL312 in subjects with C1-INH HAE.
 
3. To evaluate the safety and tolerability of CSL312 in subjects with C1-INH HAE.
 
	
 
1. Responder subjects;                             
 
HAE attack-free subjects;
 
HAE attacks;
 
HAE attacks treated with on-demand HAE medication.
 
 
 
2. CSL312 PK in plasma:                             
 
• Maximum concentration (<math>C_{max}</math>);
 
• Area under the concentration-time curve in 1 dosing interval (<math>AUC_{0-tau}</math>);
 
• Time of maximum concentration (<math>T_{max}</math>);
 
• Terminal elimination half-life (<math>T_{1/2}</math>);
 
• Total systemic clearance (<math>CL_{tot}</math>);
 
• Volume of distribution during the elimination phase (<math>V_z</math>).
 
 
 
3. Subjects experiencing:                             
 
• Adverse events (AEs);
 
• Serious AEs (SAEs);
 
• AEs of special interest (AESIs), (i.e. anaphylaxis, thromboembolic events [TEEs], and bleeding events);
 
• Injection site reactions (ISRs);
 
• Inhibitory antibodies to CSL312;
 
• Clinically significant abnormalities in laboratory assessments reported as AEs.
 
 
 

Objectives	Endpoints

CCI [REDACTED]
 
CCI [REDACTED]
	
CCI [REDACTED]
 
[REDACTED]
 
The time-normalized number of uses of on-demand HAE medication per month.
 
CCI [REDACTED]
 

CCI [REDACTED]

 
CCI [REDACTED]
 

CCI [REDACTED] (CCI [REDACTED]);

 
CCI [REDACTED]

---

Objectives	Endpoints
	CCI 

The endpoints will be evaluated separately for Treatment Period 1 and 2. Treatment Period 1 and Treatment Period 2 will be analyzed together for subjects who receive continuously the same dose of CSL312 during both treatment periods. For C1-INH subjects having a planned dose reduction from **CCI** mg to **CCI** mg in Treatment Period 2, only data until the date and time of the planned dose reduction will be included.

### 4.2.1 Primary Study Hypothesis

To test for a difference in the primary efficacy endpoint between [CCI] mg CSL312 q4wk or [CCI] mg CSL312 q4wk and placebo q4wk, pairwise comparisons will be performed by testing the hypotheses using a two-sided Mann-Whitney test.

To account for multiple testing, the alpha level of 5% will be evenly split between the two hypotheses tested. Details are given in Section 10.1.

## 4.3 Study Treatments

CSL312 will be supplied as a sterile, preservation-free solution for injection ([X] mL per vial with a concentration of [CCI] mg per [X] mL). The active substance is FXIIa antagonist monoclonal antibody. The mode of administration is IV or SC. CSL312 will be manufactured in accordance with ICH Good Manufacturing Practice guidelines and local regulatory requirements.

The placebo will be the same as the CSL312 formulation buffer and supplied in the same way as CSL312 but will not contain the active substance (FXIIa antagonist monoclonal antibody). All study administration for the blinded part in Treatment Period 1 will be volume-normalized by diluting them to the volume of the [CCI] mg dose as further explained below in Section 4.4.

### 4.3.1 On-demand HAE Therapy

Subjects must be assessed by an investigator to be capable of managing their HAE attacks during participation in the study. This must be documented by the investigator in an individual acute action plan.

Subjects may use the on-demand medication of their choice that has previously been shown to be effective to treat HAE attacks experienced during the study.

### 4.3.2 Dose Modification

No dose modification is planned in Treatment Period 1.

Subjects in Treatment Period 2 at dose of [CCI] mg CSL312 q4wk who experience  $\geq 3$  HAE attacks within an 8-week period are eligible to have their CSL312 dose increased to [CCI] mg CSL312 q4wk. All CSL312 dose increases will be made in eligible subjects at the discretion

of the investigator in consultation with CSL. All C1-INH HAE subjects receiving the [REDACTED] mg dose will have their dose reduced to [REDACTED] mg q4wk SC at their next scheduled study visit, after the subject has signed informed consent to Amendment 2.

#### 4.4 Randomization Procedures and Blinding

Randomization will be conducted using an interactive response technology (IRT).

##### *Treatment Period 1*

In Treatment Period 1, subjects will be randomized using block randomization with fixed block size by means of centralized IRT to 1 of 4 blinded treatment arms:

- The first 32 subjects with C1-INH HAE who are assigned to treatment in Treatment Period 1 will be randomized in a 1:1:1:1 ratio to receive placebo, [REDACTED] mg CSL312, [REDACTED] mg CSL312, or [REDACTED] mg CSL312 q4wk.

For the four blinded treatments above, the 32 C1-INH HAE subjects will be blinded to their treatment assignment. Except for the unblinded pharmacist (or delegate), all investigational site staff including the investigator will also be blinded to the treatment assignment of the 32 subjects with C1-INH HAE in Treatment Period 1. The unblinded personnel will prepare the investigational product but will not administer it to the subjects or assess the subjects. Representatives from CSL (or their delegates) with direct interaction with the study sites or subjects will be blinded to treatment assignment throughout Treatment Period 1. A physical blind ([REDACTED]) will be employed so that blinded study personnel or subjects are unable to detect any difference between CSL312 or placebo. Furthermore, the IV and SC doses will be volume-normalized so that irrespective of the randomized dose, the same volume will be infused or injected to each subject. The assigned IV loading doses will be diluted so that each is the same volume for administration as a dose of [REDACTED] mg (i.e., [REDACTED] mL). The assigned SC doses of CSL312 will be diluted so that each is the same volume for administration as a dose of [REDACTED] mg (i.e., [REDACTED] mL).

In addition, laboratory results which may reveal the treatment allocation will not be available to subjects, study site personnel, or CSL (and delegates) blinded to treatment assignment.

The following laboratory tests may reveal the treatment allocation:

Laboratory Category	Laboratory Test	Comments
Coagulation	CCI	Blinded in eCRF
	CCI	
	CCI	Blinded in eCRF
	CCI	
	CCI	
Immunogenicity	Inhibitory and non-inhibitory antibodies specific to FXIIa antagonist monoclonal antibody	
PK	CSL312 concentration	
CCI	CCI	
	CCI	
	CCI	
	CCI	
	CCI	
	CCI	

Up to 8 additional subjects with C1-INH HAE who are assigned to treatment in Treatment Period 1 after the first 32 subjects (above) will receive CCI mg CSL312 q2wk in an unblinded open-label manner.

Up to 10 subjects with FXII/PLG HAE who are assigned to treatment in Treatment Period 1 will receive CCI mg CSL312 q4wk in an unblinded open-label manner.

*Treatment Period 2*

In Treatment Period 2, subjects will be re-randomized using block randomization with fixed block size by means of a centralized IRT to receive either CCI mg or CCI mg CSL312 q4wk.

- For subjects with C1-INH HAE, randomization will be stratified by Treatment Period 1 treatment assignment: subjects on placebo q4wk, subjects on CCI mg CSL312 q4wk, and subjects on CCI mg CSL312 q2wk:
  - Subjects on placebo q4wk and subjects on CCI mg CSL312 q4wk will be randomized in a 1:1 ratio to receive either CCI mg CSL312 q4wk or CCI mg CSL312 q4wk in Treatment Period 2.
  - Subjects on CCI mg CSL312 q2wk will be randomized in a 1:1 ratio to receive either CCI mg CSL312 q4wk or CCI mg CSL312 q4wk in Treatment Period 2.

- Subjects with C1-INH HAE on [REDACTED] mg CSL312 q4wk in Treatment Period 1 will continue to receive [REDACTED] mg CSL312 q4wk in Treatment Period 2.
- Subjects with C1-INH HAE on [REDACTED] mg CSL312 q4wk in Treatment Period 1 will continue to receive [REDACTED] mg CSL312 q4wk in Treatment Period 2.
- Subjects with FXII/PLG HAE will continue to receive [REDACTED] mg CSL312 q4wk in Treatment Period 2.

Treatment Period 2 will be conducted in an open-label manner.

## 4.5 Determination of the Sample Size

### Subjects with C1-INH HAE

Seven subjects assigned to each treatment (placebo, or [REDACTED] mg, or [REDACTED] mg CSL312 q4wk) are needed to reach a power of ~82% for the comparisons of [REDACTED] mg CSL312 q4wk against placebo q4wk and [REDACTED] mg CSL312 q4wk against placebo q4wk in Treatment Period 1.

This is based on the following assumptions:

- Alpha is 2.5% for each of the 2 two-sided Mann-Whitney tests of [REDACTED] mg CSL312 q4wk or [REDACTED] mg CSL312 q4wk against placebo q4wk.
- The time-normalized number of HAE attacks is 2.9 attacks per month during treatment with placebo. This number was derived from CSL study CSL830\_3001, using the lower bound of the distribution-free 95% confidence interval (CI) for the median of the first placebo treatment period.
- The time-normalized number of HAE attacks is 0.6 attacks per month during treatment with [REDACTED] mg or [REDACTED] mg CSL312 q4wk. The number was derived from CSL study CSL830\_3001, using the upper bound of the distribution-free 95% CI for the median of the combined active treatment periods.
- For the time-normalized number of HAE attacks during CSL321 treatment and placebo a Poisson distribution is assumed. The lower bound and the upper bound, respectively, of the CIs for the medians are chosen for the rate parameters.
- Randomization allocation between CSL321 treatment and placebo which are compared are equal.

[REDACTED]

[REDACTED]. The sample size of 7 subjects for this arm is not driven by an

efficacy comparison, but instead, by consistency with other treatment arms and for maintenance of the blinding of the study. No testing for efficacy of the [REDACTED] mg CSL312 dose against placebo is planned and no power calculation has been done.

An additional subject will be added to each of these 4 treatment arms to account for dropouts during Treatment Period 1, resulting in 8 subjects required in each treatment arm.

Up to 7 subjects with C1-INH HAE will be assigned to receive [REDACTED] mg CSL312 q2wk. This arm is included for informational purposes, and therefore no testing against placebo is planned and no power calculation has been done. An additional subject will be added to this arm to account for dropouts during Treatment Period 1, resulting in up to 8 subjects in this treatment arm.

Overall, a total of up to 40 subjects with C1-INH HAE will be assigned to treatment in Treatment Period 1.

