10.1 Sample Size Estimation

Subjects with C1-INH HAE

Seven subjects assigned to each treatment (Placebo, or [REDACTED] mg, [REDACTED] mg, or [REDACTED] mg CSL312 q4wk) are needed to reach power of ~82% for the comparisons of [REDACTED] mg CSL312 q4wk versus placebo q4wk and [REDACTED] mg CSL312 q4wk versus placebo q4wk in Treatment Period 1. This is based on the following assumptions:

- The time-normalized number of HAE attacks is 2.9 attacks per month during treatment with placebo. This number was derived from CSL study CSL830_3001, using the lower bound of the distribution-free 95% confidence interval for the median of the first placebo treatment period.
- The time-normalized number of HAE attacks is 0.6 attacks per month during treatment with [REDACTED] mg CSL312 q4wk or [REDACTED] mg CSL312 q4wk. The number was derived from CSL study CSL830_3001, using the upper bound of the distribution-free 95% confidence interval for the median of the combined active treatment periods.
- Alpha is 2.5% for each of the 2 two-sided Mann-Whitney Tests of [REDACTED] mg CSL312 q4wk or [REDACTED] mg CSL312 q4wk against placebo.

[REDACTED]

[REDACTED]. The sample size of 7 subjects for this arm is not driven by an efficacy comparison, but instead, by consistency with other treatment arms and for maintenance of blinding of the study. No testing for efficacy of the [REDACTED] mg CSL312 dose against placebo is planned and no power calculation has been done. An additional subject may be added to each of these 4 treatment arms to account for drop outs during Treatment Period 1, resulting in 8 subjects in each treatment arm.

Up to 7 subjects with C1-INH HAE will be assigned to receive [REDACTED] mg CSL312 q2wk. This arm is included for informational purposes, and therefore no testing against placebo is planned and no power calculation has been done. An additional subject may be added to this arm to account for drop outs during Treatment Period 1, resulting in up to 8 subjects in this treatment arm.

Overall, a total of up to 40 subjects with C1-INH HAE will be assigned to treatment in Treatment Period 1.

Subjects with FXII/PLG HAE

Up to 10 subjects with FXII/PLG HAE will take part in the study.

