## 8 Data Handling Conventions

### 8.1 Missing Data

#### 8.1.1 Imputation of Non-Date Missing Data

Missing data occurs when any requested data is not provided, leading to blank fields on the collection instrument. These data will be indicated using a “blank” in subject listing displays. Answers such as “Not applicable” and “Not evaluable” are not considered to be missing data and should be displayed as such.

Only missing values for the primary efficacy endpoint (i.e., time-normalized number of HAE attacks) during Treatment Period 1 will have an impact on the analyses of the pairwise comparison between **CCI** mg CSL312 q4wk versus placebo q4wk and **CCI** mg CSL312 q4wk versus placebo q4wk in Treatment Period 1. The time-normalized number of HAE attacks will only be missing for subjects receiving investigational product q4wk and q2wk who drop out before Day 6 and Day 15, respectively, of Treatment Period 1.

Imputation methods based on Markov-Chain Monte Carlo (MCMC) techniques assume a certain distribution of the data and sample from this distribution values which are imputed to replace the missing values. With only 8 subjects per treatment, MCMC methods are not expected to yield reliable estimates. Instead a systematic approach (Enhanced Tipping Point

analysis [[Liublinska and Rubin, 2014](#)]) will be applied to investigate the robustness of the study's conclusion to the assumed missingness pattern. For details see Section [10.1.1](#).

Subjects with the assessment of treatment relationship for AEs and SAEs missing will have the worst case assumed to impute the relationship: if relationship to study treatment is missing and the event started on or after the first administration of study treatment it will be assumed to be "Yes". There will be no other imputation for missing data.

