### 8.2.8 Study Periods Relative to Treatment

The following definitions for the evaluation periods of efficacy and safety will be used to define the durations used in the denominator of the time-normalized endpoints and safety endpoints such as exposure and subject-years. It is not intended to re-assign assessments made during scheduled visits based on these definitions. Scheduled visits will not be re-labelled based on subject's study days irrespective of whether the visit takes place in the planned time window.

The Study Completion Date Visit in this study is at the end of Treatment Period 1 or Treatment Period 2 or at the time of premature study discontinuation. This visit is followed by the Follow-up Visit which may be waived in place of a telephone contact.

**Efficacy Analysis:** The evaluation periods will be:

**Run-in Period (all subjects):** From Week 1 Day 1 of the Run-in Period until the date / time of the Week 1 Day 1 Visit of Treatment Period 1 (the date / time of the first administration of

investigational product in Treatment Period 1) or the Study Completion Visit date and time (whichever occurs earlier). The duration (days) of the Run-in period will be:

Week 1 Day 1 Visit date and time of Treatment Period 1 or Study Completion Visit date and time – Week 1 Day 1 Visit date and time of Run-in + 1.

**Treatment Period 1 (subjects who receive an IV loading dose of investigational product):** From Week 1 Day 6 Visit of Treatment Period 1 (the date / time of the first SC administration of investigational product in Treatment Period 1) until the date / time of the Week 13 Day 91 Visit (the date / time of the first administration of investigational product in Treatment Period 2) or the Study Completion Visit date and time (whichever occurs earlier). The duration (days) of the efficacy evaluation period for Treatment Period 1 will be: Week 13 Day 91 Visit date and time or Study Completion Visit date and time – Week 1 Day 6 Visit date and time + 1.

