## 10.1 Primary Efficacy: Analysis of Time-Normalized Number of HAE Attacks in Treatment Period 1 (Blinded Part)

The ITT population will be used for the primary analysis and the PP will be used as the secondary.

As outlined in Section 8.2.8, HAE attacks with a start date not falling into the efficacy evaluation period will not be included in the analyses of efficacy but will be presented in a listing only.

Subjects will enter HAE symptoms into their eDiary and the start and end date and time, the interference of HAE symptom(s) with daily activities, and location(s) of the HAE symptom(s). Investigator-reported HAE attacks will be based upon review of subject diaries, relevant interval medical history, and physician judgment. The investigator may ask clarifying questions to assist in his/her assessment of whether or not an HAE attack occurred. If an attack occurred, then the investigator will record an attack in the eCRF, the start/end date, the attack location(s), and the severity of the attack based on the most severe symptoms. For every visit, the Investigator will report all HAE attacks that have occurred in the interim since the last visit the subject attended.

For the analyses, a HAE attack is defined based on the HAE attacks reported by the investigator using the HAE attack eCRF.

In the primary analysis, only subjects with C1-INH HAE who receive q4wk SC dosing (after an IV loading dose) in a blinded manner will be included. The evaluation periods are defined in Section 8.2.8.

The time-normalized number of HAE attacks per month during Treatment Period 1 for a subject will be calculated as:

$$(\text{number of HAE attacks} / \text{length of subject's evaluation period in days}) * 30.4375$$

where the length of subject's evaluation period is defined in Section 8.2.8.

The time-normalized number of HAE attacks per month will be summarized descriptively including median (primary) and mean (secondary) with corresponding 95% CIs by blinded treatment (i.e., placebo, or bci mg, bci mg, or bci mg CSL312 q4wk).

To test for a difference in the primary efficacy endpoint between [b] mg CSL312 q4wk or [b] mg CSL312 q4wk and placebo q4wk, pairwise comparisons will be performed by testing the hypotheses using a two-sided Mann-Whitney test.

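### The stated ~82% power with 7 per arm is too high for the planned Mann-Whitney test: the SAP's own Poisson inputs give about 71–76% per comparison

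*SAP*

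**What the plan says.** SAP section 4.5 opens with "Seven subjects assigned to each treatment" and says that these numbers "are needed to reach a power of ~82% for the comparisons of" the two tested doses with placebo in Treatment Period 1. Its inputs are:

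- "Alpha is 2.5% for each of the 2 two-sided Mann-Whitney tests of" the two doses against placebo.
- Rates of 2.9 attacks per month on placebo and 0.6 on either tested dose.
- "For the time-normalized number of HAE attacks during CSL321 treatment and placebo a Poisson distribution is assumed", with those two values as the rate parameters.
- Equal allocation within each comparison.

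One more subject per arm is added for dropouts, giving eight. Protocol section 10.1 and the synopsis carry the same power figure ("are needed to reach power of ~82% for the comparisons of" in section 10.1). Section 10.1 also gives the rates and alpha, but not the Poisson assumption.

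For the analysis, SAP section 10.1 says only that "pairwise comparisons will be performed by testing the hypotheses using a two-sided Mann-Whitney test". Neither document says whether p-values are exact or asymptotic, how the power was calculated, or whether power refers to each comparison, at least one, or both.

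**The concern.** With seven per arm and a low active rate, each comparison ranks 14 small counts with many ties. Large-sample power formulas for the Wilcoxon test can be well off in that setting, so ~82% needed checking against the test that will actually be run. SAP section 4.5 gives every input except the version of the test, so no outside data are needed.

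This is the only power figure given for the two confirmatory comparisons. Because the eighth subject is a dropout allowance, the plan in effect claims ~82% after losing one subject per arm. If the claim is wrong, readers are misinformed about the chance of a missed effect, and about the chance that both doses succeed in a study meant to select doses for phase 3 (Protocol section 3.3.1).

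**Working it through.** **Inputs (SAP section 4.5).** X ~ Poisson(2.9) on placebo, Y ~ Poisson(0.6) on active, 7 per arm, two-sided alpha 0.025, so z = 2.241.

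**Step 1: reproduce the stated figure.** A large-sample Wilcoxon formula on the log-odds scale comes closest.

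- P(X > Y) = 0.839 and P(X = Y) = 0.1105, so p = 0.839 + 0.1105/2 = 0.894.
- Odds = p/(1 − p) = 8.46; ln(8.46) = 2.135.
- The placement variances are 0.0322 (placebo) and 0.0141 (active). The standard error under the alternative is √[(0.0322 + 0.0141)/7] / (0.894 × 0.106) = 0.860.
- Under the null (equal mixture of the two distributions) each placement variance is 0.0792. The standard error is √[2 × 0.0792/7] / 0.25 = 0.602.
- Power = Φ[(2.135 − 2.241 × 0.602)/0.860] = Φ(0.914) = 0.820.

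The unrounded value is 81.97%, which matches ~82% with the alpha split applied. The same formula gives 76.7% for 6 per arm and 86.1% for 8. This match does not prove the source. Other approximations at n = 7 range from 62.3% (Noether) to 84.4% (normal approximation for means).

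**Step 2: power of the planned test.** 40,000 trials were simulated at each sample size, with two active arms sharing one placebo arm and each comparison tested at 0.025. Exact p-values come from the full permutation distribution with ties; asymptotic p-values are tie-corrected. The Monte Carlo standard error is about 0.2 points.

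| Evaluable per arm | Version of the test | Each | Both | At least one |
|---|---|---|---|---|
| 7 | Exact | 71.0% | 60.0% | 81.9% |
| 7 | Asymptotic, continuity-corrected | 72.3% | 61.0% | 83.7% |
| 7 | Asymptotic, uncorrected | 75.7% | 65.3% | 86.2% |
| 8 | Exact | 81.1% | 72.2% | 90.0% |
| 8 | Asymptotic, continuity-corrected | 81.2% | 72.2% | 90.2% |
| 8 | Asymptotic, uncorrected | 83.4% | 75.2% | 91.6% |

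A separately coded run gave 70.8%, 72.2% and 75.5% per comparison at n = 7, and 80.9%, 80.9% and 83.0% at n = 8.

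Other versions are lower at n = 7: 70.0% without tie correction, 65.3% without it but with continuity correction, and 53.6–58.9% with a t-approximation. No version examined reaches 80% per comparison at n = 7 and alpha 0.025.

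**Step 3: size of the gap.** 82 − 75.7 = 6.3 points and 82 − 71.0 = 11.0 points.

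**Step 4: what the dropout allowance means.** Under SAP section 8.1.1 the endpoint "will only be missing for subjects receiving investigational product q4wk and q2wk who drop out before Day 6" (q4wk) or Day 15 (q2wk). Most later dropouts therefore still contribute. With 7 evaluable in one arm and 8 in the other, the asymptotic test has 76.7–79.5% power.

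**Step 5: side check on the model.** Under SAP section 8.2.8 the evaluation runs from Day 6 "until the date / time of the Week 13 Day 91 Visit", which is 91 − 6 = 85 days, or 85/30.4375 = 2.79 months. Treating the 85-day count as Poisson gives 99.3–99.6% at n = 7 (asymptotic). Adding gamma between-subject variation with dispersion 0.25, 0.5 or 1.0 gives 82–85%, 60–64% or 34–37%. These dispersions are assumptions; the documents give none.

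**The case against.** Four points deserve an answer.

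1. **The 82% may mean at least one success.** The exact test does give 81.9% for that at n = 7. However, the text attaches power to the comparisons of each dose with placebo, sets alpha per test, and never mentions success on either dose. The per-comparison reading is the natural one. If the other was meant, the plan should say so. This part stands as a reason to define the term.

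2. **The figure comes from a recognised formula, so there is no slip.** The inputs are coherent and the formula is legitimate for large samples. But the power is claimed for a named test with seven per arm, and that test does not deliver it.

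3. **The monthly Poisson model does not describe the real endpoint, and the rates were chosen conservatively** (lower confidence bound for placebo, upper for active). This is fair: true power could be above or below 82%, and the range in step 5 is far wider than the 6–11 point gap. It limits what any single figure can mean, but it does not make ~82% correct under the model the SAP states.

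4. **The consequence is small.** This stands. Eight per arm are randomised, losses before Day 6 should be few, and no decision rule uses the power figure. It limits the importance of the point but does not make the statement right.

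**Conclusion.** The concern holds. Under the SAP's stated model, the planned test has about 71–76% power per comparison with seven evaluable per arm, not ~82%, and about 60–65% for both doses to succeed. With eight evaluable it has about 81–83% per comparison and 72–75% for both.

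This rests on three things: the monthly number being Poisson with rates 2.9 and 0.6, as SAP section 4.5 states; power being read per comparison; and the test being exact or tie-corrected asymptotic. The origin of the 82% cannot be established from the documents. The overstatement concerns the printed figure and its link to seven subjects. It does not undermine the validity of the test, the alpha split or the enrolment target. It should be corrected, but it does not threaten the trial.

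**What to change.** In SAP section 4.5, Protocol section 10.1 and the synopsis:

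- First fix the version of the Mann-Whitney test (exact or asymptotic; if asymptotic, whether continuity-corrected), and state it in SAP section 10.1 and Protocol section 10.3.2.1.1 as well.
- Replace ~82% with the exact or simulated power of that version: about 71–76% per comparison with seven evaluable per arm and about 81–83% with eight.
- Name the power method, and say whether power means each comparison, at least one, or both.

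Optionally, add power for the roughly 85-day evaluation window with a stated between-subject dispersion.

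The cost is a few sentences. The test, alpha and enrolment stay as they are. Protocol section 13.3 requires even administrative protocol changes to go to the IRB/IEC for information, so the protocol edits carry that small step. The printed power falls for seven evaluable subjects and stays near 82% for eight.
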